The current standard for definitive treatment of CECS is surgical fasciotomy of the involved compartments. According to a 2016 systematic review, surgical intervention for CECS is successful in only 66% of those affected, with 13% of patients reporting complications from surgery, and 6% needing a repeat procedure.⁵ A 2013 retrospective analysis of military members showed fasciotomy for CECS was successful in only 55% of those affected. Additionally, 28% were unable to return to full activity, 16% suffered surgical complications, and 6% underwent repeat fasciotomy. Of 661 participants, 106 were referred for medical discharge from the Armed Forces.⁶ A 2014 military cohort found 22% of patients were medically discharged or had surgical revision at short-term to mid-term follow-up. Additionally, 28% of service members were unable to return to full duty and 45% experienced incomplete relief of symptoms.⁴ Besides risks and complications, surgery also required a mean of 13 weeks to return to full activity when effective.^{7,8,9}

Formalized gait retraining is an attractive alternative to fasciotomy. It aims to influence the effect of foot contact and running kinematics to reduce leg compartment pressures which relieves pain. Diebal et al. published a case series of 10 military members with CECS who underwent a Supervised Gait Retraining (SGR) program that emphasized forefoot running. At six-weeks and one-year post-intervention, running distance, pain, and performance all significantly

improved. This case series also showed significant patient satisfaction with patients reporting 98 or better on the single assessment numeric evaluation (SANE) and 92 or better on the lower leg outcome survey.³ A 2015 prospective cohort study showed home-based gait retraining (HBGR) is an effective alternative to SGR while reducing time and invested resources.¹⁰ Despite high rates of success in limited case studies, real world application of gait retraining has limitations. Many patients struggle to make and/or sustain adaptations in their running style. Some patients have severe pain with exercise which limits efforts at effective gait re-training.

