Participants who meet final eligibility criteria (no other concomitant causes of leg pain, confirmed CECS diagnosis of the anterior and/or lateral compartments via intramuscular compartment pressure test and lower limb MRI, ABI between 0.90 and 1.40, and if applicable, negative pregnancy test) will be randomized to a study arm and their intervention dates (i.e. injection and/or supervised gait retraining) will be scheduled. Study injections (both placebo and BoNT-A) must occur within 60 days of randomization and ≥ 2 weeks post-intramuscular compartment pressure test. A computer-generated randomization program prepared by the study biostatistician will be used to assign participants uniformly across all four study arms.

Participants will be assigned to one of four treatment groups:

- Group 1 - Home Based Gait Retraining (HBGR) and Normal Saline (placebo)
- Group 2 - Supervised Gait Retraining (SGR) and Normal Saline (placebo)
- Group 3 - BoNT-A + HBGR
- Group 4 - BoNT-A + SGR

Study Intervention:

BoNT-A Injections:

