Secondary outcomes will include pain reduction according to the Numeric Pain Rating Scale (NPRS), ability to complete service specific military physical training requirements, and patient satisfaction. To assess patient satisfaction, patients will be asked if they were or were not satisfied with intervention at each follow up time point.

This will be an intention to treat study and additional data that will be collected via the Demographics CRF (Appendix C) and Baseline Data Collection CRF (Appendix D) includes:

- Standard Demographics (e.g., Age, Sex, military occupational specialty, height, weight, BMI, MOS)
- Length of military service
- Symptom duration (including length of limited duty, military profile)
- Previous Treatments
- Time to diagnosis

- Concomitant medical conditions
- Footwear characteristics and orthosis use
- Activities provoking symptoms, and perceived exertion (Borg) tolerance
- Duration of symptoms when present
- Performance on military fitness tests
- Ability to perform occupational related tasks
- Objective lower extremity strength, range of motion (ROM), ankle brachial index (ABI) blood pressure, palpation, leg length, foot parameters tests

10.3 At any point in the study, will you request, use, or access health information in any form, including verbal, hard copy and electronic?

☒ Yes ☐ No

10.4 Review the definitions below and respond to the following two questions. If you are not sure of the answers, email [contact] for assistance. The *Military Health System (MHS)* is defined as all DoD health plans and DoD health care providers that are organized under the management authority of, or in the case of covered individual providers, assigned to or employed by, the Defense Health Agency (DHA), the Army, the Navy, or the Air Force. *MHS workforce members* are employees, volunteers, trainees, and other persons whose conduct, in the performance of work for the MHS, is under the direct control of the MHS, whether or not they are paid by the MHS. *MHS business associates* are persons or entities that provide a service to the MHS and require protected health information (PHI) to provide the service.

Are you an MHS workforce member?

- ☒ Yes, I am an MHS workforce member
☐ No, I am not an MHS workforce member

10.5 Have you consulted with an MHS data expert to determine the data elements required for your study?

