In keeping with statistical analysis standards in randomized controlled trials, data will be analyzed using complete-case, intention-to-treat (ITT) analysis—that is, we will analyze all study subjects who received treatment assignment and for whom we obtained sufficient outcome data.

Confounding Variables:

Clinical effectiveness will be studied using a factorial randomized design. Such designs are widely recognized to yield unbiased estimates by removing confounding between treatment and outcome when sufficiently powered.

11.2 Sample Size:

We are requesting to enroll up to 620 participants (155 per treatment group) across all performance sites in order to evaluate a final sample of 480 subjects (120 per treatment group) across all performance sites. Up to 125 of these participants will be enrolled at WRNMMC. Up to 125 of these participants will be enrolled at each of the other performance sites.

11.3 Total number of subjects requested (including records and specimens):

620

11.4 If you are recruiting by study arm, please identify the arms of the study and how many subjects will be enrolled in each arm

Across all performance sites, up to 620 participants will be uniformly randomized across the four treatment groups: Up to 155 participants in Group 1 - Home Based Gait Retraining (HBGR) and Normal Saline (placebo), up to 155 participants in Group 2 - Supervised Gait Retraining (SGR) and Normal Saline (placebo), up to 155 participants in Group 3 - BoNT-A + HBGR, and up to 155 participants in Group 4 - BoNT-A + SGR.

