Participants may withdraw from the study at any time without penalty. Participants will be informed that withdrawal will not affect their access to health care that they are otherwise entitled to and it will not affect their military position.

If a participant withdraws from the study, we may retain and analyze all coded data collected up to the time of withdrawal if the data is necessary to maintain the integrity of the study. However, no further data will be collected after the date of withdrawal.

Participants may contact the study research coordinator or Principal Investigator to initiate the formal withdrawal process. Participants will be advised to follow-up with their personal provider if they chose to withdraw.

Withdrawal Without Participant Consent:

Participants will be removed from the study if they fail to meet the formal screening criteria outlined in protocol section 13.3.

Additionally, a participant may be withdrawn from the study without their consent if remaining in the study might be dangerous or harmful to them. Participation may also be stopped if the military mission requires it, if they lose their right to receive medical care at a military hospital, if the study is canceled, if they fail to adhere to the protocol and/or therapy plan, or if they display inappropriate behavior towards study personnel.

The reason for any withdrawal/removal will be documented (see Appendix S).

14.0

Risks and Benefits

14.1

Risks of Harm:

Identify all research-related risks of harm to which the subject will be exposed for each research procedure or intervention as a result of participation in this study. Consider the risks of breach of confidentiality, psychological, legal, social, and economic risks as well as physical risks. Do not describe risks from standard care procedures; only describe risks from procedures done for research purposes

With the exception of the injection itself, all of the study activities are regularly performed in a standard clinical environment as procedures and treatment for CECS of the anterior and/or lateral compartments in the lower leg, therefore the potential risks directly associated with study-specific activities and procedures are minimal. However, there are standard risks common with some of these procedures.

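### The analysis labelled intention-to-treat is complete-case, and removal for non-adherence can make the missing outcomes informative

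*Combined protocol and SAP*

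**What the plan says.** Section 10.2 declares: "This will be an intention to treat study". Section 11.1, under Missing Data and Outliers, states that "data will be analyzed using complete-case, intention-to-treat (ITT) analysis" and explains this as: "we will analyze all study subjects who received treatment assignment and for whom we obtained sufficient outcome data". It does not say what counts as sufficient. It names no imputation method, no missing-data assumption and no sensitivity analysis.

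Section 13.6 lists grounds on which participation may be stopped without the participant's consent, among them "if they fail to adhere to the protocol and/or therapy plan". Under voluntary withdrawal, the same section lets the study keep data already collected but adds that "no further data will be collected after the date of withdrawal".

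Three other passages bear on who ends up with outcome data:

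- Section 10.1, Randomization: "Study injections (both placebo and BoNT-A) must occur within 60 days of randomization". Follow-up visits are then counted from the injection.
- Section 10.1, on participants who move or cannot attend: a list of data to be collected remotely. It includes questionnaires but does not name the 2-mile run.
- Section 9.2, on gait retraining: "Many patients struggle to make and/or sustain adaptations in their running style".

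**The concern.** Intention-to-treat means that everyone randomised is counted in the assigned arm, with a stated way of handling missing outcomes. Section 11.1 keeps the assigned arm but drops whoever lacks enough data. Because enough is undefined, the analysis set could be settled after the data have been seen.

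This matters more because the protocol can itself create the missing data. A participant who does not follow the therapy plan can be removed, and such a participant may well be one for whom treatment is failing. Adherence is also easier to observe in the supervised arms, where sessions are documented, than in the home-based arms, which have one in-person session and later contacts. Blinding covers only saline versus BoNT-A. Loss could therefore differ by arm and be related to outcome, and a complete-case comparison is then biased.

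**Working it through.** **1. The plan's own allowance.** Sections 11.2 and 11.5 give a final sample of 480, roughly 20% attrition and 620 enrolled. 480 / (1 − 0.20) = 600, or 150 per arm, of whom 30 per arm would have no outcome. The other 20 of the 620 (3.2%) are left for screen failures, for which no rate is stated. The 620 is therefore plausible but cannot be fully reproduced.

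**2. How loss turns into bias.** Let p be the true success rate in an arm, m the share missing and q the success rate among the missing. The complete-case rate is (p − m·q) / (1 − m). If m and q are the same in two arms with the same p, the difference is 0 and the false-positive rate stays at 5%. Bias under no effect needs m or q to differ between arms.

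**3. Illustration A: one arm loses failures only.** Assumptions: 155 per arm, same true rate in both arms, 10% of one arm (16 people) removed, all failures, no loss in the other arm, two-sided pooled two-proportion z test at 5%. The spurious difference is p × 155/139 − p = p × 16/139.

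| True rate | Spurious difference | False positives |
|---|---|---|
| 15% | 1.7 points | 7% |
| 40% | 4.6 points | 13% |
| 50% | 5.8 points | 17.5% |
| 80% | 9.2 points | 58% |

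The rates 15%, 50% and 80% are planning rates from section 11.5; 40% is an added intermediate value.

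**4. Illustration B: both arms lose people, unequally.** Assumptions: 150 per arm, 15% missing in one arm and 25% in the other, missing participants succeeding half as often, unpooled Wald test. At p = 50%: (0.50 − 0.15 × 0.25)/0.85 = 0.544 and (0.50 − 0.25 × 0.25)/0.75 = 0.583, a spurious 3.9 points with 9.4% false positives. At 15% the result is 1.2 points and 5.7%; at 80% it is 6.3 points and 38%.

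**5. Worst-case bounds.** Assume 20% missing in each arm and observed rates equal to the planned ones. The lower bound for arm B minus arm A is 0.8·pB − (0.8·pA + 0.2), and the upper bound is (0.8·pB + 0.2) − 0.8·pA.

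| Comparison | Planned | Bounds (points) |
|---|---|---|
| Group 4 vs 3 | 85% vs 80% | −16 to +24 |
| Group 2 vs 1 | 50% vs 15% | +8 to +48 |
| Group 3 vs 1 | 80% vs 15% | +32 to +72 |
| Group 4 vs 2 | 85% vs 50% | +8 to +48 |

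Only group 4 versus 3 can change sign. Its planned difference of 5 points is also about the size of the bias from a small loss: removing 8 failures of 155 from one arm at 80% gives 0.80 × 8/147, about 4.4 points.

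**6. Two further gaps in outcome data.** Visits are counted from injection, so someone randomised but never injected has no visit schedule. The 2-mile run is part of the primary outcome (10.2), and passing the Army 2-mile test is the sample-size endpoint (11.5). The remote list does not name it, so it may be missing for those who relocate.

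**The case against.** A reader might infer that the analysis is close to per-protocol. The documents do not support that. Section 11.1 selects on assignment and outcome data, not on treatment received. Section 10.1 keeps participants who cross over, even to fasciotomy, in follow-up. Removal is discretionary, its frequency is not stated, and earlier data may be retained. Section 10.14 asks for remote data when a visit cannot be attended. Non-adherent participants who stay are analysed as assigned.

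A reader might also infer that the bias favours supervised retraining. The remark in 9.2 about patients struggling concerns gait retraining in general, and all four arms receive some form of it. No arm-specific loss is given. Disappointed participants in group 1, expected to succeed least at 15%, could equally be the ones to leave, which would reverse the sign.

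Two statements must stay inferences. The sentence ending data collection stands under voluntary withdrawal and is not repeated under removal without consent; applying it there is reasonable but not explicit. No text excludes the never-injected or establishes that relocated participants lose the run outcome: the follow-up form asks about service-specific training requirements, and records may be reviewed. These are gaps, not demonstrated exclusions.

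The scenarios are assumed, and illustration A is deliberately one-sided. Worst-case loss at the planned 20% could not reverse three of the four planned differences. All of this stands. It limits the size and direction that can be claimed, but it does not supply a definition of sufficient, a missing-data method or a sensitivity analysis.

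**Conclusion.** The point holds in this form: the analysis is complete-case, not the full intention-to-treat analysis promised in 10.2, and discretionary removal for non-adherence can make missingness depend on adherence and outcome. Under no true effect, the spurious difference ranges from 0 (equal, similarly selected loss) to 9.2 points in illustration A. Its direction cannot be known from the documents. Group 4 versus 3 is the most fragile comparison. The size rests on assumed loss patterns, since only an overall attrition of roughly 20% is given. Outcomes that are never collected cannot be recovered at analysis, so section 13.6 needs attention as well as the analysis plan.

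**What to change.** 1. In section 13.6, separate stopping study therapy from leaving follow-up. Non-adherence should not end outcome collection unless the participant withdraws consent. State explicitly whether the no-further-data sentence covers removals. This concerns data collection only; the grounds for stopping therapy are a separate matter.
2. In section 11.1, analyse everyone as randomised, including those never injected, and give a stated anchor date for their visits (for example the scheduled injection date). Add a question on the 2-mile run to the remote data list.
3. Define sufficient outcome data, and pre-specify a missing-data method that uses arm, site, baseline values and outcomes from other visits, for example multiple imputation.
4. Add sensitivity analyses: complete-case, missing counted as failure, and a delta-adjusted or tipping-point analysis. The last is needed because standard imputation assumes data are missing at random and does not address loss driven by the unseen outcome.

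The cost is a short change to 13.6, new wording in 11.1, and somewhat more follow-up and analysis work. Effect estimates may turn out less favourable.

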11.5 Please provide a justification for your sample size

Using a 2x2 factorial design and assuming success rates for passing the US Army 2-mile run test among control (saline/home based gait retraining), botulinumtoxin A (BoNT-A) injection, supervised gait retraining (SGR), and combined therapy (BoNT-A + SGR), respectively, are 15%, 80%, 50%, and 85%, we estimate that enrolling a grand total of at least 60 patients would yield 80% power to detect the effect of BoNT-A, enrolling a grand total of at least 120 patients would yield 80% power to detect the effect of SGR, and enrolling a grand total of at least 380 patients would yield 80% power to demonstrate the benefit of combined therapy (BoNT-A + SGR) vs. either therapy in isolation. If we can obtain complete data on more than 380 participants, then it will strengthen our power. We hope to have a final sample of 480 participants. Assuming roughly 20% attrition and accounting for screen failures, we are requesting to enroll up to 620 participants across all performance sites.

Power was estimated using Monte Carlo simulations assuming uniform randomization among four groups in the 2x2 factorial design, while testing for statistical significance simultaneously among the four groups of control, BoNT-A, SGR, and combined therapy using a generalized linear model. Statistical significance was indicated if the corresponding $p < 0.05$ per generalized linear model.

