At 8 weeks (+/- 1 week), 3 months (+/- 2 weeks), 6 months (+/- 2 weeks), and 12 months (+/- 2 weeks) post-injection, participants will undergo Balance Error Scoring System (BESS) testing, objective foot parameters, ankle strength, range of motion (ROM), ankle brachial index (ABI) blood pressure, and palpation tests, and a gait and run analysis using advanced wearable technology as part of a self-paced treadmill test until cessation or the successful completion of a two-mile run (whichever occurs first). A gait analysis Data Collection CRF (Appendix R) will be used to collect some of the gait analysis from the advanced wearable technology and will be completed after the participant's visit.

Participants will also be asked about involvement in non-study related activities and treatments including acupuncture/acupressure, aquatics, anti-inflammatory/pain medication, athletic taping, change in running shoes, chiropractor, dry needling, electrical stimulation, foot orthotics, gait retraining, ice pack/massage, massage, physical therapy, strengthening, stretching, yoga, and other treatments.

Intramuscular compartment testing of participant's anterior and lateral compartments will be re-tested at 6 months (+/- 2 weeks) post-injection. The same compartments tested at baseline or at a previous test 6 months prior to consent of the study, will be recollected at the 6 month time point.

Results of the in-person clinical assessments and the intramuscular compartment testing will be recorded in the Follow Up Data Collection CRF.

Overall, the 8 week, 3 month, 6 month, and 12 month follow up activities will take approximately 2.5 hours each and the 24 month follow up activities will take approximately 30 minutes each.

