Blinding will be revealed to the participants after all the components of the 3 month follow-up visit have been completed. Participants who are not satisfied with their treatment results and/or who are unable to complete a 2-mile run without producing pain and/or symptoms will be offered the option to receive BoNT-A injections and/or Supervised Gait Retraining if they had not received those active treatments.

At the 6 month follow-up visit, participants who are still not satisfied with their treatment results and/or still unable to complete a 2-mile run will be offered any remaining treatment option, including surgical fasciotomy which is offered as standard of care. Participants who express interest in surgical fasciotomy will be referred to an orthopaedic surgeon who will dictate and guide this treatment option. Further details and scheduling will be per the orthopaedic surgeon's recommendations. Patients who cross over to alternative treatment options (including surgical fasciotomy) will remain in the study and will continue to follow up with the research team at the intervals listed above.

Data Entry:

With the exception of the Intake CRF which collects participant contact information, all coded research data will be entered into REDCap, an encrypted, access controlled, password protected electronic data capture and management system housed on a DoD server and maintained by the Uniformed Services University (USU). No PII will be entered into REDCap. See Appendix J for additional information on REDCap. See Appendix I for a PDF copy of the REDCap forms for this study.

Additional Info - MIRROR/USU:

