There will be appropriate data sharing agreements in place between the data owner(s) (e.g., DHA for AHLTA) and the Walter Reed National Military Medical Center (WRNMMC), as well as the Uniformed Services University (USU) and all appropriate parties involved in the handling of data (e.g., The Geneva Foundation).

10.2 Data Collection:

Describe all the data variables, information to be collected, the source of the data, and how the data will be operationally measured.

Please see attached Data Collection Schedule (Appendix H).

The local study team will collect study data directly from the study participant, from their attending provider or, where applicable, from the participant's medical record (i.e., relevant medical and treatment history and relevant clinical notes) and record it on paper CRFs (see Appendixes A-F). Study completion will be documented (see Appendix S). The completed paper CRFs will serve as source documents for this study. Participants may also enter study data directly into REDCap using a coded survey link. In these cases, the completed eCRFs will be printed and stored in the participant's research files and serve as source documents. Other source documents include relevant laboratory results (i.e., hCG urine test) and relevant clinical notes which will be printed, redacted, and stored in the participant's research file.

With the exception of the Informed Consent Form, HIPAA Authorization, and Intake CRF (Appendix B) which collects contact information, all paper CRFs will be identified using a unique study ID only, and not by the participant's name, social security number, DoD ID, or other protected identifier.

The primary outcome will be functional improvement via statistical changes in the Balance Error Scoring System (BESS), University of Wisconsin Running Injury and Recovery Index (UWRI), Single Assessment Numerical Evaluation (SANE), Patient Specific Functional Scale (PSFS), Global Rate of Change (GROC), objective data from the gait and run analyses (e.g., average vertical load rate, cadence, foot pattern strike, etc.), ability to return to full active duty, and ability to complete a 2-mile run. Full active duty is defined as meeting all service specific requirements of physical training and ability to complete work duties with either no pain or pain that is tolerable as determined by the patient.

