12.4 Special categories, check all that apply

- ☐ Minors /Children
- ☐ Students
- ☐ Employees - Civilian
- ☐ Employees - Contractor
- ☐ Resident/trainee
- ☐ Cadets /Midshipmen
- ☒ Active Duty Military Personnel
- ☐ Wounded Warriors
- ☐ Economically Disadvantaged Persons
- ☐ Educationally Disadvantaged Persons
- ☐ Physically Challenged (Physical challenges include visual and/or auditory impairment)
- ☐ Persons with Impaired Decisional Capacity
- ☐ Prisoners
- ☐ Pregnant Women, Fetuses, and Neonates
- ☐ Non-English Speakers
- ☐ International Research involving Foreign Nationals - Headquarters Review is necessary

You must also consider the requirements of DoDI 3216.02, Enclosure 3, paragraph 7.e.

12.5 Inclusion Criteria:

Order Number	Criteria
1	Active duty service member age 18-60 (inclusive).
2	Fluent in speaking and reading English
3	Unable to run 2 miles without producing pain and/or symptoms, including aching, burning, numbness, tingling, and/or weakness in the affected limb.
4	Has difficulty completing the running portion of their service specific physical training due to pain and/or symptoms in the affected limb.

5	Meets clinical diagnostic criteria for CECS of the anterior and/or lateral compartment(s) in the lower leg, per clinical exams (e.g., physical examination, intramuscular compartment pressure test (IMCP test needle testing), lower leg MRI, etc.).
---	---

12.6 Exclusion Criteria:

Order Number	Criteria
1	Prior Botulinum toxin injection(s) in the lower leg compartments of the affected limb.
2	Prior compartment release of the affected limb.
3	Recent (within the last 6 months) lower limb injury that needed medical intervention
4	Undergone formal gait retraining within the last 6 months.
5	Allergic to BoNT-A (trade names BOTOX® or Xeomin®)
6	Pregnant or breastfeeding.
7	Medical history and/or clinical exams (e.g., physical examination, intramuscular compartment pressure test, lower limb MRI, amyotrophic lateral sclerosis (ALS), myasthenia gravis, Lambert-Eaton Syndrome, or any neuromuscular junction disorders) indicate other more likely causes of leg pain and/or symptoms.
8	Ankle Brachial Index (ABI) blood pressure ≤ 0.90 or ≥ 1.4 within the last 6 months. Post Exertion ABI is >0.2 or limb pressure decreases > 30 mmHg.

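### Patient numbers rest on US Army 2-mile test pass rates, but the primary run outcome is completing 2 miles, which some eligible participants may already do at baseline

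*Combined protocol and SAP*

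**What the plan says.** The documents describe running ability in several ways.

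- **Sizing (11.5).** Power is simulated "assuming success rates for passing the US Army 2-mile run test among control" and active arms. The rates "respectively, are 15%, 80%, 50%, and 85"% are for control, BoNT-A, SGR and combined therapy, and no source is given. The stated totals for 80% power are 60 (BoNT-A), 120 (SGR) and 380 (combined against either alone). A final sample of 480 is hoped for.
- **Primary outcome (10.2).** The list includes "ability to complete a 2-mile run" among several measures. An Army test pass is not on it.
- **Run performed (10.1, baseline and the visits from 8 weeks to 12 months).** A "self-paced treadmill test until cessation or the successful completion of a two-mile run (whichever occurs first"). No time standard or symptom condition is attached.
- **Service fitness tests.** Section 9.3 plans to assess each participant against their own service's standards. Section 10.1 collects this by asking. Section 10.2 makes it a secondary outcome and also builds it into the definition of full active duty, which is a primary component.
- **Eligibility (12.5).** Criterion 3 reads "Unable to run 2 miles without producing pain and/or symptoms". Criterion 4 asks for difficulty, not inability, with the running part of service training.
- **Treatment offers (10.1, Study Blinding).** The 3-month rule covers participants "unable to complete a 2-mile run without producing pain and/or symptoms". The 6-month rule refers to being unable to complete 2 miles and omits the symptom condition.
- **Analysis (11.1).** A logistic model with three group indicators. Neither the binary outcome nor the time point is named.

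**The concern.** Power calculated for one endpoint carries over to another only if the success rates carry over. Passing a service test and finishing 2 miles at one's own pace are different events, and the plan gives no reason to expect the same rates.

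The entry criteria sharpen the problem. Someone who can finish 2 miles in pain satisfies criterion 3, and the baseline test itself allows for successful completion. On a simple completion outcome, such a participant would be a success before treatment in whichever arm they joined. That raises the control rate and shrinks every between-arm difference.

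Because 11.1 names no outcome, the analysis section does not settle which definition is meant. The choice of run endpoint could then be made after the data are seen.

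**Working it through.** **1. The plan's own figures.** I simulated the 11.1 logistic model on the stated rates (Wald test, two-sided 0.05, uniform allocation). BoNT-A against control has 81.7% power at a total of 60, and SGR against control has 82.0% at 120. Both agree with the stated 80%. The 380 figure does not reproduce for combined therapy against BoNT-A (85% v 80%), which has about 14% power there. That weakness exists whichever run endpoint is used, so it is a separate matter.

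**2. Illustrating the endpoint change.** Inputs from 11.5: p = 0.15, 0.80, 0.50 for control, BoNT-A and SGR. Assumption: a share b of enrolled participants completes 2 miles at baseline and again at follow-up, and the rest succeed at the planned rates. Then

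p′ = b + (1 − b)p, and each difference shrinks by the factor (1 − b).

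| b | Control | SGR | BoNT-A | SGR − control | BoNT-A − control |
|---|---|---|---|---|---|
| 0 | 15% | 50% | 80% | 35 | 65 |
| 0.2 | 32% | 60% | 84% | 28 | 52 |
| 0.4 | 49% | 70% | 88% | 21 | 39 |
| 0.6 | 66% | 80% | 92% | 14 | 26 |

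**3. Power formula.** With n per arm, d the difference and p̄ the mean of the two rates:

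power = Φ{(d − 1.96·SE₀)/SE₁}, SE₀ = √[2p̄(1 − p̄)/n], SE₁ = √{[p₁(1 − p₁) + p₂(1 − p₂)]/n}.

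Example, SGR at b = 0.4 and n = 120: d = 0.21, p̄ = 0.595, SE₀ = 0.0634, SE₁ = 0.0619. So (0.21 − 0.1242)/0.0619 = 1.386 and power = 92%.

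**4. Results, SGR against control.**

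| b | Total 120 (30 per arm) | Total 380 (95 per arm) | Total 480 (120 per arm) |
|---|---|---|---|
| 0 | 84% | >99% | >99% |
| 0.2 | 59% | 98% | 99% |
| 0.4 | 38% | 84% | 92% |
| 0.6 | 23% | 59% | 69% |

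Simulating the logistic model at the same rates agrees within about 2 points (for example 58%, 37% and 21% at 120).

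**5. BoNT-A against control.** Even at b = 0.6, power is 99.5% at 380 and 99.9% at 480. I do not use the formula at a total of 60: with 15 per arm it gives 98% on the stated rates against the simulated 82%.

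**The case against.** Much can be said for the plan.

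- **Treadmill completion is not the only thing measured.** Service-test ability is collected and sits inside a primary component through full active duty, so the sizing endpoint has a relative among the primary outcomes. This stands. But it is each participant's own service test, obtained by asking, and not the Army test for everyone.
- **No section says a baseline completer is scored as a success.** Section 10.2 speaks of improvement and statistical change, and reading its 2-mile item as the treadmill test is an inference. This stands, and it shows that the outcome is not defined. Criterion 4 also makes easy completers less likely, though difficulty is not inability.
- **The planned sample has slack.** This also stands. At 480, SGR against control drops below 80% only at the top of the assumed range.

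A reader might go further and infer that the planned rates and powers are wrong, or that the trial is underpowered for its main contrasts. The documents do not support that. They give no 2-mile completion rate, and the only pre-treatment running figure (9.2) concerns one mile and severe pain. A reader might also infer that one participant could be both a primary success and a declared treatment failure at 3 months. Section 10.1 sets a rule for offering further treatment there; it does not define an endpoint.

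**Conclusion.** The mismatch is in the text and needs no assumption: 11.5 is sized on an event that is not a listed outcome, while the listed run outcome and the run performed are something else. Eligibility leaves room for baseline completion. The 15/80/50/85% rates, and the powers built on them, are therefore unsupported for the measured run outcome. They have not been shown to be false.

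The size of the effect rests on two assumptions: the 20–60% range for baseline completion, and planned rates holding in everyone else. Within that range the stated 120 for SGR is fragile. The intended 480 copes up to 40%. The 380 that 11.5 treats as the minimum copes up to 40% with less margin. BoNT-A against control is not threatened at either total. This should be corrected, but it does not undermine the whole design.

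**What to change.** Name one binary run outcome and one time point, in the same words, in 10.2, 11.1 and 11.5.

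- **Preferred:** completing the 2-mile treadmill run without the symptoms listed in inclusion criterion 3. Every participant is then a non-success at entry by eligibility. The drawback is that it is partly self-reported. Follow-up already asks about leg symptoms when running. The case report forms were not available, so one added item at the end of the treadmill run may or may not be needed. Keep simple completion and own-service test ability as secondary outcomes.
- **If simple completion is kept:** add baseline treadmill completion or distance, already collected, to the logistic model. If nearly all baseline completers complete again, a completion indicator will cause separation, so the plan should say how the model would then be fitted.

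In either case, justify success rates for the chosen outcome and do not carry over the Army-test rates. Restate power at 380 and 480. The 3-month and 6-month wording in 10.1, with and without the symptom condition, must be reconciled.

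The cost is wording in three sections, a new power run and possibly one form item.
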